### Setting/Participants:

The study setting will be the apheresis unit, the outpatient day hospital or the inpatient units at the Children's Hospital of Philadelphia.

There will be two sites: The Children's Hospital of Philadelphia, New York Blood Center.

We will recruit 20 subjects overall from The Children's Hospital of Philadelphia. The first 5 subjects enrolled will be adults.

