## **3 INVESTIGATIONAL PLAN**

### **3.1 General Schema of Study Design**

There will be a screening and baseline assessment, and a treatment phase. See Table 1 for an overview of the study visits and procedures.

We will enroll at least 5 adults to collect safety and preliminary efficacy data, before enrolling children to the study. The data gathered will be submitted to the IRB via an amendment to be reviewed by the convened board. We will obtain IRB approval before opening enrollment to children.

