### **3.2.2 Total Number of Study Sites/Total Number of Subjects Projected**

The study will be conducted at 2 investigative sites in the United States. The Children's Hospital of Philadelphia, and The New York Blood Center (no subject enrollment, providing *RH* genotyped red cell units and engaged in research activities).

Recruitment will stop when approximately 20 subjects are enrolled. It is expected that approximately 20 subjects will be enrolled to produce 18 evaluable subjects.

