### **3.3.1 Inclusion Criteria**

- 1) Males or females age  $\geq$  8 years.
- 2) Diagnosis of SCD, all genotypes
- 3) Requires chronic red cell transfusion therapy
- 4) Requires a minimum of 3 units per transfusion visit

---

- 5) History of anti-D
- 6) *RH* genotype predicts D+ expression
- 7) Anti-D not detectable at screening visit and past 6 months

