**Table 2. Laboratory monitoring**

	Pre-transfusion	Immediate Post-transfusion	5-12 days Post-transfusion
Complete blood count	✓	✓	✓
Hemoglobin quantification	✓	✓	✓
Reticulocyte count	✓		✓
Antibody screen/identification	✓		✓
Bilirubin (total, unconjugated)			✓
Creatinine			✓
Plasma sample frozen	✓		✓
Donor red cells frozen	✓		

Any time a patient shows a re-appearance of anti-D on an antibody screen, the medical monitor will be notified, and all safety data will be reviewed. As stated above, if a subject re-demonstrates anti-D, we will end that subject's participation and he/she will resume transfusions with D negative RBC units.

If any subject shows signs of transfused red cell hemolysis, with or without an anti-D identified on the antibody screen, the medical monitor will be notified, and all safety data will be reviewed.

Study stopping criteria include:

- 1) Two of the first 5 enrolled subjects, or after the first 5 enrolled subjects, greater than 30% of enrolled patients, develop re-appearance of anti-D
- 2) Any subject with anti-D re-appearance and clinical or laboratory evidence of transfused red cell hemolysis (dark urine, increased scleral icterus, exacerbated anemia, higher Hb S level than expected based on timing from last transfusion

If either of these criteria occur, the study will be stopped, the safety medical monitor will review all clinical and laboratory evidence to determine safety risks, and will meet with the investigative team to determine a safe course of action. The IRB would be notified and the study procedures would be suspended until approval of the IRB.

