## 8 SAFETY MANAGEMENT

### 8.1 Clinical Adverse Events

Clinical adverse events (AEs) will be monitored throughout the study.

We will have a medical monitor independent of the study team who is familiar with SCD and transfusion, and blood bank procedures. The medical monitor will review safety data, including antibody screens for anti-D reappearance, and other laboratory studies, i.e blood counts and hemoglobin quantifications, for signs of transfused red cell hemolysis. Details about the units transfused, including the *RH* genotype, and the red cell antigen profile, will be reviewed.

Any time a patient shows a re-appearance of anti-D on an antibody screen, the medical monitor will be notified, and all safety data will be reviewed. As stated above, if a subject re-demonstrates anti-D, we will end that subject's participation and he/she will resume transfusions with D negative RBC units.

If any subject shows signs of transfused red cell hemolysis, with or without an anti-D identified on the antibody screen, the medical monitor will be notified, and all safety data will be reviewed.

Study stopping criteria include:

- 1) Three of the first 5 enrolled subjects, or greater than 50% of enrolled patients, develop re-appearance of anti-D
- 2) Any subject with anti-D re-appearance and clinical or laboratory evidence of transfused red cell hemolysis (dark urine, increased scleral icterus, exacerbated anemia, higher Hb S level than expected based on timing from last transfusion)

If either of these criteria occur, the study will be stopped, the safety medical monitor will review all clinical and laboratory evidence to determine safety risks, and will meet with the investigative team to determine a safe course of action. The IRB would be notified and the study procedures would be suspended until approval of the IRB.

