### 9.3 Regulatory and Ethical Considerations

#### 9.3.1 Data and Safety Monitoring Plan

The study has greater than minimal risk. The study intervention of *RH* genotype matched D+ red cells to patients with SCD and anti-D provides a higher level of matching than current standard of care, but there is a risk of anti-D reappearance, increased red cell hemolysis and delay to transfusion for up to 7 days. If a patient re-demonstrates anti-D, we will end that subject's participation and he/she will resume transfusions with D negative RBC units. In the case of acute need for transfusion, subjects may receive non-*RH* genotype matched red cells that would be matched by standard of care methods at the discretion of the attending physician, i.e. D-, CEK matched red cells. Oversight for the emerging safety information will include the PI. Red cell units will continue to be issued per standard institutional blood bank policies.

---

We will have a medical monitor independent of the study team who is familiar with SCD and transfusion, and blood bank procedures. The medical monitor will review safety data, including antibody screens for anti-D reappearance, and other laboratory studies, including blood counts and hemoglobin quantifications, for signs of transfused red cell hemolysis. Details about the units transfused, including the *RH* genotype, and the red cell antigen profile, will be reviewed.

Any time a patient shows a re-appearance of anti-D on an antibody screen, the medical monitor will be notified, and all safety data will be reviewed. As stated above, if a subject re-demonstrates anti-D, we will end that subject's participation and he/she will resume transfusions with D negative RBC units.

If any subject shows signs of transfused red cell hemolysis, with or without an anti-D identified on the antibody screen, the medical monitor will be notified, and all safety data will be reviewed.

Study stopping criteria include:

- 1) Two of the first 5 enrolled subjects, or after the first 5 enrolled subjects, greater than 30% of enrolled patients, develop re-appearance of anti-D
- 2) Any subject with anti-D re-appearance and clinical or laboratory evidence of transfused red cell hemolysis (dark urine, increased scleral icterus, exacerbated anemia, higher Hb S level than expected based on timing from last transfusion)

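### Stopping criterion 1 counts adults and children together and its early limb can be met only by adults, so the anti-D limit that applies to children depends on what happened in the adults

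*Combined protocol and SAP*

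**What the plan says.** Section 4.2, in the stopping criteria after Table 2, states criterion 1 as "Two of the first 5 enrolled subjects, or after the first 5 enrolled subjects, greater than 30% of enrolled patients, develop re-appearance of anti-D". Section 9.3.1 repeats it: "Two of the first 5 enrolled subjects, or after the first 5 enrolled subjects, greater than 30% of enrolled patients". Section 8.1 has other thresholds: "Three of the first 5 enrolled subjects, or greater than 50% of enrolled patients, develop re-appearance of anti-D". None of the three separates adults from children.

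The order of enrolment is fixed elsewhere. The Abstract (Setting/Participants) says "The first 5 subjects enrolled will be adults", and section 3.1 says "We will enroll at least 5 adults to collect safety and preliminary efficacy data, before enrolling children to the study". The adult data go to the convened IRB, and section 3.1 adds "We will obtain IRB approval before opening enrollment to children". On numbers, section 3.2.2 says "It is expected that approximately 20 subjects will be enrolled to produce 18 evaluable subjects".

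Sections 6.1 and 6.2 treat anti-D re-appearance, hemolysis and timely provision of units as descriptive outcomes and plan no breakdown by age group.

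**The concern.** The plan puts adults first so that safety data exist before any child is exposed. Criterion 1 does not follow that logic through. Its small-number limb covers the first five enrolled, who are all adults, and it is used up before a child enters. What remains for children is a percentage of everyone enrolled. Each adult without anti-D enlarges the denominator, so a reassuring adult lead-in loosens the limit for children, while a single adult event tightens it sharply.

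At stake is the only study-level limit on anti-D re-appearance without hemolysis. If several of the first children re-formed anti-D, whether the study stopped would turn partly on the adult results. Because section 6 also plans only pooled description, the final report need not show the two groups apart.

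**Working it through.** **Inputs.** Thresholds: 2 of the first 5, then more than 30% of enrolled (4.2, 9.3.1); 3 of the first 5, or more than 50% (8.1). At least 5 adults come first (3.1). About 20 are enrolled in all (3.2.2), hence at most 20 − 5 = 15 children. The protocol gives no stopping probability to reproduce and no numerical anti-D risk; section 9.3.2 only predicts that the risk is very low. The risks used below are therefore assumptions.

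**Boundary.** I read the percentage limb cumulatively. With n enrolled, the smallest count above 30% is floor(0.30n) + 1: 2 at n = 6; 3 at n = 7 to 9; 4 at n = 10 to 13. Above 50% it is floor(0.50n) + 1. Subtracting the adult events leaves the child events needed. A dash means the limb cannot fire at that point.

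| Adults (events), limb | 1 child | 2 | 3 | 4 | 5 | 6 | 10 |
|---|---|---|---|---|---|---|---|
| 5 (0), >30% | – | – | 3/3 | 3/4 | 4/5 | 4/6 | 5/10 |
| 5 (1), >30% | 1/1 | 2/2 | 2/3 | 2/4 | 3/5 | 3/6 | 4/10 |
| 8 (0), >30% | – | – | – | 4/4 | 4/5 | 5/6 | 6/10 |
| 10 (0), >30% | – | – | – | – | 5/5 | 5/6 | 7/10 |
| 5 (0), >50% | – | – | – | – | – | 6/6 | 8/10 |
| 5 (1), >50% | – | – | – | 4/4 | 5/5 | 5/6 | 7/10 |

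Checks: 2/7 = 28.6%, no stop; 3/8 = 37.5%, stop; 2/6 = 33.3%, stop. Under 8.1, 5/10 = 50% is not above 50%, while 6/11 = 54.5% is.

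**How likely each adult history is.** With assumed adult risk p, P(0 of 5) = (1−p)^5 and P(1 of 5) = 5p(1−p)^4. For p = 5, 10, 20, 30 and 40%, the first is 77, 59, 33, 17 and 8%, and the second is 20, 33, 41, 36 and 26%. Both histories are realistic.

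**Chance of stopping under criterion 1.** Assumptions: five adults, children enrolled one at a time with each result known before the next, independent events with common risk q, and the 4.2 thresholds used only for illustration. By the fifth child:

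- Pooled, no adult event: P(at least 3 of 4) = 4q³(1−q) + q⁴. At q = 0.10 this is 0.0036 + 0.0001 = 0.4%; at q = 0.40 it is 0.1536 + 0.0256 = 17.9%.
- Children also counted alone, no adult event: P(at least 2 of 5) = 1 − (1−q)^5 − 5q(1−q)^4. This gives 8.1% at 0.10 and 66.3% at 0.40.
- Pooled, one adult event: q + (1−q)[3q²(1−q) + q³]. At 0.10: 0.10 + 0.90 × 0.028 = 12.5%. At 0.40: 0.40 + 0.60 × 0.352 = 61.1%.
- Both counts, one adult event: q + (1−q)P(at least 2 of 4). At 0.10: 0.10 + 0.90 × 0.0523 = 14.7%.

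Over 15 children, stepping exactly through the same boundaries:

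| Adult events | Child risk | Pooled only | Pooled plus children-only |
|---|---|---|---|
| 0 | 10% | 0.9% | 13.2% |
| 0 | 40% | 60.4% | 90.5% |
| 1 | 10% | 14.3% | 18.8% |

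At the same 40% child risk, the pooled rule stops by the fifth child with probability 17.9% or 61.1%, depending only on whether no adult or one adult had an event.

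**The case against.** A reader might infer that the rule can never fire on the first two children. The documents do not support that. One event in five adults does not meet the early limb of 4.2, enrolment continues, and the first child's anti-D then stops the study. The result holds only when no adult has had an event, or when enough further adults have been enrolled.

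A reader might also infer that children are unprotected, or that they carry a different risk. Neither is documented. Any single anti-D event goes to the medical monitor with review of all safety data, and that subject's participation ends. One subject of any age with anti-D and hemolysis stops the study under criterion 2. The convened IRB sees the adult data before any child enrols and could set paediatric conditions. A cluster in children would be seen. Nothing in the protocol says that recurrence differs with age, and a 40% risk in children is an assumption for illustration. These points lower the severity. They do not supply a study-level limit: criterion 2 needs hemolysis, discontinuation protects one subject, and the IRB step looks at adult data.

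Replacing the pooled count with separate counts would be a mistake. After one adult event and at 10% child risk, the children-only count stops by the fifth child with probability 8.1%, below the 12.5% of the present rule.

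Lastly, the percentage limb could be read as covering only patients enrolled after the first five. Then 1/1, 1/2 or 1/3 would fire and the dilution would vanish. The wording refers to enrolled patients in general, so the cumulative reading is the more natural one, but the text does not settle it.

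**Conclusion.** The concern holds in conditional form. Criterion 1 pools ages, and its early limb can be met only by adults. With five event-free adults and a cumulative denominator, the 30% limb cannot fire on the first two children and then needs 75 to 100% of the first three to five. With ten event-free adults it cannot fire before 5 of 5, and under the 8.1 version with five event-free adults not before 6 of 6. With one adult event among five, the 30% limb fires on the first child. The limit for children is therefore set partly by the adult results.

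The boundary counts are exact, given the cumulative reading and everyone enrolled being exposed and assessed. Counting enrolled subjects who have not yet been transfused would make firing harder still. The stopping probabilities rest on assumed risks. Severity is moderate: the other safeguards are real, but none of them is a study-level limit on anti-D without hemolysis in children.

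**What to change.** Use the amendment already required before children enrol.

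1. Reconcile criterion 1 across sections 4.2, 8.1 and 9.3.1, and with the adults-first design in the Abstract and section 3.1. State whether the count pools ages and who is in the denominator.
2. Keep the pooled count and also count children on their own, so that protection is never lower than now. The thresholds for both are for the sponsor and IRB to decide.
3. In section 6.2, report anti-D re-appearance, hemolysis and feasibility for adults and children separately as well as overall.

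The drafting cost is a sentence or two in each place. The operating cost is more pauses for review when the true risk in children is low. At an assumed 10% risk with five adults and the 4.2 thresholds for illustration, the chance of a pause becomes 8% instead of 0.4% by the fifth child, and 13% instead of 1% over 15 children, if no adult had an event. After one adult event it becomes 15% instead of 12.5%, and 19% instead of 14%. The 8% by the fifth child equals what the first five adults already face at that risk under 4.2.

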### **3.3.2 Exclusion Criteria**

- 1) Rare *RH* genotype that would preclude sufficient RBC units
- 2) Antigen negative requirements due to alloimmunization that would preclude sufficient RBC units
- 3) Parents/guardians or subjects who, in the opinion of the Investigator, may be non-compliant with study schedules or procedures.

Subjects that do not meet all of the enrollment criteria may not be enrolled. Any violations of these criteria must be reported in accordance with IRB Policies and Procedures.

For subjects with a history of stroke/recurrent transient ischemic attack or other indication who require tight control of Hb S and *RH* genotyped blood is not available, standard of care serologic matched blood would be administered rather than delaying transfusion and risking higher Hb S level.

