## **4 STUDY PROCEDURES**

### **4.1 Screening Visit and Baseline Assessment**

The screening visit and baseline assessment will occur on the same day with the following procedures:

[figure not shown]
- Informed consent
- Review inclusion/exclusion criteria
- Demographics/medical history
- Medication review
- Physical exam
- Vital signs
- Laboratory test review
- Medical Record Review

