### **4.2 Study Treatment Phase**

Intervention visits will be scheduled with each of the subject's transfusion visits as per the subject's clinical indication for chronic transfusion therapy. We will provide one unit of D+ *RH* genotype matched RBCs at the first transfusion study visit (Figure 3). The remainder of units will be D-, CEK-matched, and negative for all other antigens the patient is alloimmunized

---

against. In this manner, should anti-D be re-stimulated, only one unit of the 3 to 11 units required for red cell exchange will be at risk for hemolysis, and the patient would not become

**Figure 3. Example transfusion protocol for D+ patient with history of anti-D** that is not currently detectable, and requires 6 units per RBC exchange every 3 weeks. One D+ unit will be matched by *RHD* genotype and transfused at the first two study visits, and an increasing number of D+ units will be issued at consecutive RBC exchange visits. U, unit. Triangle denotes a study visit for laboratory studies including an antibody screen, CBC, hemoglobin quantification and bilirubin level

acutely anemic. If laboratory monitoring shows no anti-D re-appearance or signs of increased hemolysis, the patient will receive one unit of D+ *RH* genotype matched RBCs at the 2nd transfusion study visit, and again if no anti-D re-appearance or signs of increased hemolysis, we will increase by one D+ unit per study visit until all units are D+. If a patient re-demonstrates anti-D, we will end that subject's participation and he/she will resume transfusions with D negative RBC units.

All patients with SCD on chronic transfusion therapy have a pre-transfusion complete blood count (CBC), Hgb quantification to determine %hgb A and S levels, and an antibody screen. We will collect a pre-transfusion sample to prospectively store plasma on all study subjects. Patients undergoing chronic red cell exchange will have an immediate post-procedure CBC and hgb quantification as standard of care. Study participants will return 5-12 days post-transfusion for a CBC/reticulocyte count, hgb quantification, bilirubin level, and antibody screen to evaluate for anti-D recrudescence or red cell hemolysis (Table 2).

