## **9.5 Informed Consent/Accent and HIPAA Authorization**

All prospective subjects eligible for participation in this study will be enrolled after obtaining informed consent. The study coordinator or one of the investigators will obtain consent in the Hematology Clinic, Day Hospital, or Apheresis Unit. The consent process will take place in the clinic exam room, or other private room where privacy is assured. The investigational nature of the study, the study objectives, procedures involved and the potential risks and benefits will be explained to the subject and/or guardian using lay language. Consent forms will be written in a well-organized format using direct language. We will explicitly state that the choice of study participation will not impact their access to clinical care. Assent will be obtained from all children seven years and older before study enrollment when deemed appropriate by the investigator and the parent(s). Written informed combined consent/HIPAA authorization and assent (if applicable) will be obtained. Individuals with limited English proficiency will only be enrolled in person after obtaining written consent using the short form consent process.

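### The anti-D stopping limit is counted over enrolled subjects, not those given a D+ unit and then screened, so it is generally looser than its nominal value

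*Combined protocol and SAP*

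**What the plan says.** The study stopping criteria appear three times.

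- **Section 4.2 (below Table 2) and section 9.3.1:** criterion 1 is met by two of the first five enrolled subjects or, after those five, when "greater than 30% of enrolled patients, develop re-appearance of anti-D" (section 4.2). Section 9.3.1 says the same: "after the first 5 enrolled subjects, greater than 30% of enrolled patients, develop re-appearance of anti-D".
- **Section 8.1:** three of the first five enrolled, or "greater than 50% of enrolled patients, develop re-appearance of anti-D".

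All three count over enrolled subjects. The timing of enrollment relative to exposure comes from other sections:

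- Section 9.5: "All prospective subjects eligible for participation in this study will be enrolled after obtaining informed consent". Section 3.3.2 adds "Subjects that do not meet all of the enrollment criteria may not be enrolled". Consent and eligibility review both fall at the screening visit (section 4.1).
- The first D+ unit is given at a later scheduled transfusion visit, and visits are typically 3 to 5 weeks apart (sections 3.1.2 and 4.2). The antibody check follows: "Study participants will return 5-12 days post-transfusion".
- A subject may get standard serologic units at a visit if matched units cannot be found in time (3.1.2), may withdraw (4.5), or may be taken off study for repeated missed visits (7.1.4).
- Section 3.2.2 expects about 20 enrolled to yield 18 evaluable. The term evaluable is not defined.

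Criterion 2 stops the study at any one subject with anti-D re-appearance and evidence of hemolysis of transfused cells.

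**The concern.** The rule is meant to limit how often D+ study units bring anti-D back. A subject who has not had such a unit, or has had one but not yet the later screen, cannot contribute an event caused by the intervention, yet enlarges the denominator. The observed rate among those actually at risk can then exceed the stated limit without criterion 1 being met. Criterion 1 is the only numeric limit on the re-appearance rate, and section 9.3.2 names re-appearance as a principal risk. What is at stake is a late or missed suspension for a run of anti-D re-appearances without hemolysis; those with hemolysis are caught by criterion 2.

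**Working it through.** **Plan's own figure.** The plan gives bare thresholds, with no assumed anti-D rate and no operating characteristics, so there is no calculated figure to reproduce. At full enrollment, more than 30% of 20 means 7 events, since 6/20 = 30.0% does not exceed the limit.

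**Events needed.** For a denominator n, events needed = floor(0.30 × n) + 1. Taking n as enrolled (as written) or as exposed and screened:

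| Enrolled | Screened | Needed, enrolled | As share of screened | Needed, screened |
|---|---|---|---|---|
| 20 | 19 | 7 | 36.8% | 6 (31.6%) |
| 20 | 18 | 7 | 38.9% | 6 (33.3%) |
| 20 | 15 | 7 | 46.7% | 5 (33.3%) |
| 20 | 10 | 7 | 70.0% | 4 (40.0%) |
| 10 | 6 | 4 | 66.7% | 2 (33.3%) |

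With exactly one unexposed subject, the two counts differ at only 5 of the 15 enrollment totals from 6 to 20 (7, 10, 14, 17 and 20). With the section 8.1 limit, floor(0.50 × n) + 1, they differ at every even total from 6 to 20.

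**Stopping probability, some subjects never exposed.** Assumptions, none of them in the plan: 20 enrolled, one independent risk per exposed subject, results read without lag, exposure in enrollment order, and the never-exposed equally likely to hold any position. Both clauses are applied after each subject, by exact calculation.

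| Thresholds | Assumed risk | Never exposed | Screened denominator | Enrolled denominator |
|---|---|---|---|---|
| 4.2 / 9.3.1 | 20% | 1 | 45.1% | 41.6% |
| 4.2 / 9.3.1 | 20% | 2 | 44.5% | 38.1% |
| 4.2 / 9.3.1 | 30% | 1 | 76.0% | 72.3% |
| 4.2 / 9.3.1 | 30% | 2 | 74.9% | 68.2% |
| 8.1 | 50% | 1 | 74.1% | 68.2% |
| 8.1 | 50% | 2 | 72.6% | 61.7% |

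D+ exposure rises over visits, so a single risk per subject is a simplification and these figures are good only to a few points.

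**Stopping probability, waiting time only.** Suppose everyone is eventually exposed and only the wait from enrollment to first screen matters. Take that wait as 3.7 weeks (3 weeks + 5 days) to 7.7 weeks (5 weeks + 7 days' delay + 12 days). At 30% risk and the 4.2 thresholds, the screened denominator gives 76.0%. By simulation, the enrolled denominator gives about 73 to 75% at 4 random enrollments a year (20 over 5 years). At 20 a year it gives about 66 to 70%. Section 6.3 says 20 to 25 such patients are already active, so fast early enrollment is possible. The only enrollment gate is at least five adults, with IRB approval, before children (3.1).

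**Cases where the rule as written is tighter.**
- Section 4.2 and Table 2 require a pre-transfusion antibody screen. With 6 enrolled and 5 screened, take one event after exposure and one on a pre-transfusion screen before any D+ unit. Over enrolled, 2/6 = 33.3% meets the limit; over exposed, 1 of 5 does not.
- Suppose events occur in the 1st and 5th enrolled, and the 5th enrolled is the 8th exposed. Two of the first five enrolled meets the rule. In exposure order it is one of the first five and 2/8 = 25%, which does not.

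**The case against.** The best case for leaving the text alone is that little depends on it. This is a descriptive pilot, and criterion 1 triggers suspension and review, not a test. Every re-appearance goes to an independent medical monitor and ends that subject's participation. Criterion 2 does not use a denominator, and the IRB sees the adult data before children enroll. The exclusions also reduce non-exposure for want of blood: rare *RH* genotypes are kept out, as is "Antigen negative requirements due to alloimmunization that would preclude sufficient RBC units". If matching failed independently at 15% of visits (the edge of the feasibility limit in 6.1), three failures in a row would have probability 0.15³ = 0.34%, or about 0.07 of 20 subjects. All of this stands, and it keeps the point minor.

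Section 6.2.3 bases the safety analysis on subjects entered at Visit 1, which section 4.2.1 makes the first D+ transfusion. That is close to an exposed population. But Table 1 labels screening as Visit 1, and nothing ties this population to the stopping rule, so it does not settle the denominator.

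It is also fair that the base-case gap of 3.7 points (76.0 against 72.3%) is about as large as the precision of the model, and that the conflict between 4.2/9.3.1 and 8.1 moves the limit more than the denominator does.

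A reader might infer three stronger things that the documents do not support:
- That the limit can only ever be looser. The two counterexamples in the working show otherwise.
- That the loosening is always slight. That depends on an accrual pace the plan does not fix.
- That the gap between 20 enrolled and 18 evaluable means two subjects will go unexposed. The plan does not say what makes a subject evaluable.

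**Conclusion.** The point holds as a minor defect of definition. As written, criterion 1 is generally looser than its nominal limit, because its denominator includes subjects not yet at risk or not yet observed. The size runs from nil, if every enrolled subject has been exposed and screened when the rule is read, through one event and roughly 4 to 7 percentage points of stopping probability at an assumed 30% risk with one or two never exposed, to three events at 20 enrolled and 10 screened. The first two depend on assumed risks and the last on an assumed accrual pace; the plan states neither. That the denominator is enrolled subjects, and that enrollment precedes exposure, is plain from the text. It does not follow that subjects go unprotected: the practical gap is confined to anti-D without hemolysis, which the monitor still reviews case by case.

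**What to change.** First reconcile the thresholds in sections 4.2 and 9.3.1 with those in 8.1; this review takes no position on which is right. In the same edit, whichever thresholds result:

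- Count the percentage over subjects who have received at least one D+ study unit and had a later antibody screen.
- Define the first five as the first five such subjects, in order of first D+ unit.
- Count as events the re-appearances found after the first D+ unit, and keep reporting any earlier anti-D to the medical monitor.

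This is a change of wording. Unit disposition and antibody screens are already recorded. The cost is a somewhat greater chance of suspension for review, including when the true risk is below the limit. Under the 4.2/9.3.1 thresholds with one subject never exposed, it is 45.1% instead of 41.6% at an assumed 20% risk, and 13.4% instead of 12.1% at 10%.
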